6.3.3.2. Sputum sample quality

Sputum sample quality will be summarized (squamous cell count, neutrophils cells count and bacteria direct smear) at any stable visit and at any mild, moderate or severe AECOPD visit. Sputum sample characteristics will be also summarized by bacterial and /or viral presence in any stable visit and in any exacerbation visit.

Sputum quality, derived as detailed in section [11.2.3](#), will be tabulated given the type of visit.

6.3.4. Incidence rates of AECOPD

This study will provide an estimate of average number of exacerbations per person per year, in a COPD population at increased risk of exacerbation (i.e. moderate to very severe COPD patients with a documented history of at least 1 moderate or severe AECOPD in the year prior to enrolment).

To compute the incidence rate all the exacerbations will be taken into account. The observation period is from visit 1 to visit 3 or from visit1 to the last visit performed for patients lost to follow up.

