8.2. Subject withdrawal

Subjects who are withdrawn because of AEs or SAEs related to study participation must be clearly distinguished from subjects who are withdrawn for other reasons.

From an analysis perspective, a 'withdrawal' from the study refers to any subject who did not come back for the concluding contact foreseen in the protocol.

All data collected until the date of withdrawal/last contact of the subject will be used for the analysis.

A subject is considered a 'withdrawal' from the study when no study procedure has occurred, no follow-up has been performed and no further information has been collected for this subject from the date of withdrawal/last contact.

Investigators will make an attempt to contact those subjects who do not return for scheduled visits or follow-up. The mode of contact will be by telephone. Three phone contacts will be made with an interval of one week between each phone call.

Information relative to the withdrawal will be documented in the eCRF. The investigator will document whether the decision to withdraw a subject from the study was made by the subject himself/herself or by the investigator, as well as which of the following possible reasons was responsible for withdrawal:

- SAE.
- Non-serious AE.
- Protocol violation (specify).
- Consent withdrawal, not due to an AE*.
- Moved from the study area.
- Lost to follow-up.
- Other (specify).

*In case a subject is withdrawn from the study because he/she has withdrawn consent, the investigator will document the reason for withdrawal of consent, if specified by the subject in the eCRF.

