6.3.4.4. Statistical methods: analysis of count data with overdispersion

The incidence rate and its 95% CI will be estimated using the Generalised Linear Model (GLM) assuming a negative binomial distribution for the response variable with logarithm as link function and the logarithm of follow up time as an offset variable. The fit of the model will be examined using Q-Q plots of standardised residuals. It is possible that the negative binomial model will not converge due to underdispersion of data; in such cases, to overcome the problem of underdispersion, a Poisson model will be used to obtain the incidence rate and its 95% CI.

SAS codes:

```
proc genmod data = <dataset>;
  class gold age smoking exacHist;
  model n_exac = GOLD age smoking exacHist country
    / link=log dist=negbin offset=logfuinyears ;
  ods output parameterestimates=out_parm nobs=nobs;
  ods exclude modelinfo modelfit parameterestimates nobs;
  run;

  data parm_est(keep= val rate rate_ll rate_ul);
    set out_parm(where=(parameter='intercept'));
    format rate rate_ll rate_ul 8.2;
    val= "mean number per year from negative binomial model without
covariate";
    rate=exp(estimate);
    rate_ll=exp(lowerwaldcl);
    rate_ul=exp(upperwaldcl);
  run;
```

where GOLD = COPD grade (2, 3 or 4), age = age at enrolment (40-49, 50-59, 60-69, ≥ 70 years), smoking = smoking status at enrolment (current and former smokers), exacHist = number of exacerbations reported in the 12 months prior to enrolment (one, two and equal or above three), country = countries in the study (Hong Kong, Philippines, Korea, Taiwan), n_exac = number of exacerbations during the study and logfuinyears = logarithm of the follow-up period in years.

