6.3.5.2.1. Statistical methods: survival analysisKaplan-Meier curves

Kaplan-Meier survival curves will be produced to represent the cumulative survival probability over time.

The code follows.

```
Proc lifetest data = <dataset> method = KM plot = (S, LLS);  

  time survt*Status(0);  

  strata smoking;  

run;
```

where survt = survival time in days (days to first exacerbation, for censored data the date of last contact will be used), status = censoring variable (0 = censored, 1 = event), and smoking = smoking status at enrolment (current and former smokers). The PLOTS=(S,LLS) option produces log-log curves as well as survival curves.

Cox Proportional Hazards regression model

To investigate the effect of several baseline risk factors upon the time to first exacerbation, Cox Proportional Hazards (PH) regression models will be fitted.

SAS codes

```
Proc phreg data = <dataset>;  

  class GOLD age exacHist sex  

  model survt*Status(0) = gold age exacHist / ties = exact rl;  

  strata smoking;  

run;
```

where GOLD = GOLD grade (2,3 or 4), age = age at enrolment (40-49, 50-59, 60-69, ≥ 70 years), smoking = smoking status at enrolment (current and former smokers), exacHist = number of exacerbations reported in the 12 months prior to enrolment (one, two and equal or above three) and sex (male and female). For the scope of the example, the variable *smoking* is considered to be a stratification factor.

Recurrent event survival analysisSAS code

```
Proc phreg data = <dataset> covs(aggregate);  

  model (start,stop)*event(0) = exacerbationHistory smoker;  

  id pid;  

run;
```

The code (START,STOP)*EVENT(0) in the MODEL statement indicates that the time intervals for each observation are defined by the variables START and STOP and that EVENT = 0 denotes a censored observation.

CONFIDENTIAL201112 (EPI-NTHI-001 BOD APA)
Statistical Analysis Plan Amendment 2 Final**6.3.6. Impact of AECOPD on HRQOL**

Descriptive statistics (N, mean, median, SD, minimum, maximum, first and third quartiles) on the CAT and SGRQ-C scores (total score and symptoms, activity and impacts component scores) will be tabulated at each stable scheduled visit, overall and by COPD GOLD grade at enrolment.

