CAT and SGRQ-C (total score and symptoms, activity and impacts component scores) changes from first visit to final scheduled visit will be displayed according to the number of exacerbation occurred in the observation period. Correlation will be evaluated using Spearman's rank-order correlation coefficient.

Descriptive statistics (N, mean, median, SD, minimum, maximum, first and third quartiles) on the CAT score will be tabulated for any stable and any mild, moderate or severe exacerbation visit.

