6.3.8. Impact of AECOPD on healthcare utilisation

Descriptive statistics of the daily number of healthcare utilisation (number of HCU in the relevant period divided by the number of days) within the stable period and within the exacerbation period will be presented overall and divided by the following unscheduled visits:

1. Number of physician office consultations,
2. Number of visits to urgent care,
3. Number of visits to emergency department,
4. Number of hospitalizations.

Healthcare use for each patient will be obtained through review of the patient's medical record (aided by patient daily self-reporting in the eDiary).

Healthcare utilisation will be summarized according to country and COPD grade at enrolment. In addition, healthcare utilisation will be summarized by AECOPD severity during exacerbations.

Overall HCU [total number and divided by type of HCU] per patient will be correlated to the number of exacerbations experienced during the observation time.

Current medication for COPD and additional COPD treatments prescribed by primary and secondary care physicians within the stable period and within the exacerbation period will be described by drug category (chronic use for COPD and chronic use for other

CONFIDENTIAL

201112 (EPI-NTHI-001 BOD APA)
 Statistical Analysis Plan Amendment 2 Final

disorders) overall, by country and by COPD grade at enrolment. In addition, percentage of patients with or without inhaled corticosteroids at enrolment and incidence rate of confirmed exacerbation by use of corticosteroids will be tabulated.

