6.4.5. Microbiome analysis

Further characterization of *H. influenzae*, *M. catarrhalis* and HRV strains will be performed. Details of the statistical analyses will be released in a separate additional analysis request.

CONFIDENTIAL201112 (EPI-NTHI-001 BOD APA)
Statistical Analysis Plan Amendment 2 Final**6.4.6. Biomarkers**

Descriptive statistics (N, mean, median, SD, minimum, maximum, first and third quartiles) for the level of each quantitative biomarker/haematology parameter will be tabulated for visit 1 and visit 3. The difference in sample mean will be reported together with a confidence interval.

Number and percentage of patients with fibrinogen, human serum C reactive protein (hsPCT), C-X-C Motif Chemokine Ligand 10 (CXCL10) values outside the laboratory normal ranges will be tabulated for visit 1 and visit 3.

Descriptive statistics will be presented overall and by GOLD grade at enrolment.

Changes in biomarkers will be evaluated according to the number of exacerbations occurred in the observation period using Pearson's correlation coefficient (or Spearman's rank-order correlation coefficient if the normal distribution assumption is not met).

The mean number of exacerbations per year overall, by severity of exacerbation and by presence of Hi and Mcat in the sputum collected at exacerbation visits will be calculated for patients with blood eosinophil levels $\geq 2\%$ and for those with blood eosinophil levels $< 2\%$ (the level measured for each patient at visit 1 will be used for this categorization).

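### SAP 6.3.4 ends AECOPD person-time at the last visit performed, in conflict with protocol 8.2 and the SAP's own survival censoring, and does not tie counted events to that window

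*SAP*

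**What the plan says.** SAP 6.3.4 has two sentences on the point. On the numerator: "To compute the incidence rate all the exacerbations will be taken into account". On the denominator: "The observation period is from visit 1 to visit 3 or from visit1 to the last visit performed for patients lost to follow up". The model in SAP 6.3.4.4 uses "the logarithm of follow up time as an offset variable" and does not define the end of follow-up.

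Two other places use a different end date. Protocol 8.2: "All data collected until the date of withdrawal/last contact of the subject will be used for the analysis". SAP 6.3.5.2.1, on time to first exacerbation: "for censored data the date of last contact will be used". SAP section 9 lists no change from the planned analyses.

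Protocol 8.2 lists seven reasons for withdrawal, of which loss to follow-up is one. Protocol 3.1.1.1 records confirmed AECOPDs from the screening visit, whereas person-time in 6.3.4 starts at Visit 1.

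**The concern.** Scheduled visits are six months apart, but symptoms are recorded daily in the diary, so a patient who leaves between visits has observed time after the last scheduled visit. Section 6.3.4 can be carried out in three ways:

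- **A:** AECOPD visits count as visits. Follow-up is then lengthened only in leavers who have an event, and it ends at that event.
- **B:** only scheduled visits count, but events after the last one are kept.
- **C:** only scheduled visits count, and events are cut at the same date.

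A and B bias the rate upward; C discards observed time. Under B or C, a patient who leaves between Visit 1 and Visit 2 has zero follow-up. The same happens under A if the patient has had no AECOPD visit. The log offset is then undefined and the patient drops out of the model. The rate is reported overall and by GOLD grade, severity, country and pathogen, so two programmers could produce different sets of tables from the same text.

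**Working it through.** **The plan's precision.** Protocol Table 13 uses variance Φn/T². For a rate of 1 and T = 160 (80% of 200), the half-width is 1.96 × √(Φ × 160)/160 = 0.155, 0.190 and 0.219 for Φ = 1, 1.5 and 2. This reproduces the printed intervals 0.85-1.15, 0.81-1.19 and 0.78-1.22.

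**Inputs.** From the documents: visits at 0, 0.5 and 1 year; daily diary; 80% completion (protocol 9.2), so at most about 20% non-completers. Assumed: a share d of patients leaves at times uniform over the year and unrelated to risk; the true rate is 1 per year; every AECOPD has a visit. The values d = 5% and 10% are illustrative. The value 20% applies the rule to all planned non-completers.

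**Reference.** Person-time per patient to the date of leaving is (1 − d) + 0.5d = 1 − 0.5d, and expected events are the same number.

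**Reading C.** Leavers contribute 0.25 year on average (half contribute 0.5, half 0), so person-time is 1 − 0.75d. Events are cut likewise, so there is no bias. Share of time discarded = 0.25d/(1 − 0.5d):
- 5%: 0.0125/0.975 = 1.3%
- 10%: 0.025/0.95 = 2.6%
- 20%: 0.05/0.90 = 5.6%

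**Reading B.** Person-time is 1 − 0.75d. If all events are kept, including those of patients with zero follow-up, the ratio to truth is (1 − 0.5d)/(1 − 0.75d):
- 5%: 0.975/0.9625 = +1.3%
- 10%: 0.95/0.925 = +2.7%
- 20%: 0.90/0.85 = +5.9%

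If zero-time patients drop out with their events, as in a log-offset model, events are (1 − d) + 0.5d × 0.75 = 1 − 0.625d. The ratios are 0.96875/0.9625, 0.9375/0.925 and 0.875/0.85, or about +0.7%, +1.4% and +3%. A simulated negative binomial fit with dispersion 0.5 to 1.0 (assumed) gives about +0.8%, +1.6% to +1.8% and +3.4% to +3.9%, inside these ranges.

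**Reading A.** The expected time from the last visit of any kind to leaving is the average of 1 − e^(−s) over s from 0 to 0.5, which is 1 − (1 − e^(−0.5))/0.5 = 0.213. Leavers with zero follow-up have no events, so the ratio is (1 − 0.5d)/(1 − 0.713d):
- 5%: 0.975/0.964 = +1.1%
- 10%: 0.95/0.929 = +2.3%
- 20%: 0.90/0.857 = +5.0%

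The simulated negative binomial fit raises these to about +1.6%, +3.2% and +7.0% at dispersion 1.0.

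**Zero follow-up, if such patients stay in the FAS.** Under B or C, 0.5d: 2.5%, 5% and 10% of patients. Under A, d × (1 − e^(−0.5)) = 0.393d: about 2%, 4% and 8%.

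**Literal last contact.** Suppose every leaver is next reached when the following scheduled visit is missed (assumption). Counting that call as follow-up adds 0.25d of unsurveilled time. The ratio (1 − 0.5d)/(1 − 0.25d) gives −1.3%, −2.6% and −5.3%.

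**The case against.** **The plan probably means C.** This is a strong point. SAP 6.3.6 has changes that "will be displayed according to the number of exacerbation occurred in the observation period"; 6.3.8 has healthcare use that "will be correlated to the number of exacerbations experienced during the observation time"; 6.4.6 says "Changes in biomarkers will be evaluated according to the number of exacerbations occurred in the observation period". The two sentences of 6.3.4 are adjacent, and nothing says that events outside the period are counted. A reader might infer from the wording on all exacerbations that the planned rate is inflated by up to 6% or 7%. The documents do not support that: on the favoured reading there is no bias, and the upper figures need reading A or B together with 20% drop-out. What stands is that 6.3.4 does not exclude A or B, and that C still discards observed time.

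**Other withdrawals may be covered.** A reader might infer that six of the seven withdrawal categories have no rule. Protocol 8.2 treats as withdrawn, for analysis, anyone who did not return for the concluding contact, so loss to follow-up may have been meant to cover all non-completers. The protocol also uses the term as a separate category, so the SAP should say which is meant.

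**Zero follow-up may not arise.** The FAS excludes patients who discontinued at Visit 1. If patients lost between Visits 1 and 2 are coded there, none remains with zero time. SAP 5.4.3 and section 6 do not say how they are coded.

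**Ending at a visit is defensible, and protocol 8.2 is not an ideal standard.** SAP 12.4 includes events reported retrospectively at scheduled visits, so ascertainment is fullest there. Last contact taken literally would include bare phone calls and could bias the rate downward by as much as A or B bias it upward. A reader might conclude that copying the protocol's date is enough; it is not. The date needs an operational definition.

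**The endpoint is secondary and descriptive.** That is so, and it limits the weight of the point.

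**Conclusion.** The inconsistency is real: one SAP gives two end dates for the same exacerbations, and one of them departs from protocol 8.2 without being declared. The numerical effect is modest: nil to about +7%, with the top of the range reached only under reading A at 20% drop-out and high dispersion. At 5% to 10% drop-out the bias is at most about 3%, against a planned half-width of 15% to 22% of a rate of 1. Table 13 is unaffected. The sizes rest on uniform, non-informative drop-out, a rate of 1 and the assumed dispersion; the documents give no withdrawal dates. The text should be changed so that the rate is reproducible, uses the observed time and agrees with the survival analysis. The documents do not show that the planned rate is materially wrong.

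**What to change.** In SAP 6.3.4, for every withdrawal whatever the reason, define follow-up as running from Visit 1 to the earlier of Visit 3 and the last date on which exacerbation status was ascertained. That is the last diary entry, or the last visit or recorded contact at which exacerbations since the previous assessment were reviewed. Count only exacerbations with onset in that interval, which also removes those between screening and Visit 1. Use the same date in the Kaplan-Meier and Cox analyses, the rate tables and the four-week correction in 11.3. State that this makes the protocol's last contact operational by leaving out calls that only establish contact or withdrawal, because they add unsurveilled time. State also how patients lost between Visits 1 and 2 are coded.

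The cost is a short SAP edit and one derived date, applied in several analyses. Intermediate AECOPD calls are held only in source documents (protocol Table 5 footnote), so the date would rest on diary, visit and recorded end-of-AECOPD call data.

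Small biases remain. If 10-20% of events are captured only retrospectively (assumption), the rate is too low by that fraction of the time after the last scheduled visit: at most 5.6% × 20% = 1.1%, at 20% drop-out. If diaries stop two to four weeks before a patient leaves (assumption), a later AECOPD visit still lengthens follow-up only in patients with an event; simulation puts this at +0.2% to +1.5% over 5% to 20% drop-out.

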6.3.4.1. Overall incidence

The following incidence rates (per patient per year) will be computed, with 95% CIs [using negative binomial regression detailed in section [6.3.4.4](#)]:.

- Confirmed exacerbations (exacerbation events confirmed by the investigator plus missed exacerbation visits with medical records: 5 and 6 dash boxes for the former and 2 and 7 for the latter from [Figure 1](#)).
- Confirmed exacerbations plus potential exacerbations with alert confirmed by phone call/or at the study site (potential exacerbations correspond to 3 dash box in Figure 1).
- Exacerbation events with sputum sample positive for selected pathogens

CONFIDENTIAL

201112 (EPI-NTHI-001 BOD APA)
 Statistical Analysis Plan Amendment 2 Final

The incidence rate of confirmed exacerbations and of confirmed exacerbations plus potential exacerbations confirmed by phone call/or at the study site, with 95% CIs, will be estimated according to COPD severity at enrolment based on GOLD classification [GOLD 2, 3, 4].

The incidence rates of confirmed exacerbations, with 95% CIs, will be also computed by exacerbation severity.

In addition, the incidence rates of confirmed exacerbations, with 95% CIs, will be estimated according to covariates such as sex, country, age at enrolment (below median age or equal to/above median age), smoking status at enrolment (current and former smokers) and number of exacerbations reported in the 12 months prior to enrolment (one, two and equal or above three).

6.3.4.2. Incidence bacteria/viruses associated AECOPD

The following incidence rates (per patient per year) will be computed, with 95% CIs:

- AECOPD events with sputum sample containing bacterial pathogens found by culture or by PCR (overall and by, but not limited to, the following bacterial species: *H. influenzae* (and *H. influenzae* after differentiation from *H. Haemolyticus* by PCR assay), NTHi (after differentiation from typeable *H. influenzae* by PCR assay), *M. catarrhalis*, *S. pneumoniae*, *S. aureus*, and *P. aeruginosa*).
- AECOPD events with sputum sample containing viral pathogens found by PCR (overall and by, but not limited to, the following viral species: RSV, parainfluenza virus, enterovirus/ HRV, metapneumovirus, influenza virus, adenovirus, bocavirus and coronavirus using qualitative PCR and HRV also by quantitative RT-PCR).

These incidence rates, with 95% CIs, will be estimated also according to covariates such as COPD severity, sex, country, age at enrolment, smoking status at enrolment and number of exacerbations reported in the 12 months prior to enrolment.

In addition, incidence rate of mild, moderate and severe exacerbation having sputum containing any bacterial/viral pathogen will be computed overall and by species.

Incidence rate of AECOPD overall and associated to bacteria (detected by culture and by PCR) will be computed also at interim analysis.

6.3.4.3. Analyses of exacerbations in relation to morning e-diaries

Among morning e-diary alerts the frequency distribution of the following groups will be tabulated (refer to [Figure 1](#) dashed boxes):

1. Potential event not confirmed by phone call/or at the study site (unconfirmed alerts, box 1),
2. Potential event confirmed by phone call/or at the study site, without site visit, with medical records confirming exacerbation (missed AECOPD visits with medical records, box 2),

CONFIDENTIAL201112 (EPI-NTHI-001 BOD APA)
Statistical Analysis Plan Amendment 2 Final

3. Potential event confirmed by phone call/or at the study site, without site visit and without medical records (missed AECOPD visits without medical records, box 3).
4. Potential event confirmed by phone call/or at the study site, with site visit but not confirmed by study investigator (unconfirmed AECOPD visit, box 4),
5. Potential event confirmed by phone call/or at the study site, with site visit and confirmed by study investigator (AECOPD event, box 5),

[figure not shown]
Reasons for inconsistencies between morning e-diary alert and no confirmation by phone call, reasons for missing study visit after phone call confirmation, and reasons for inconsistencies between phone call confirmation and study visit will be tabulated.

In absence of morning diary alert the percentage of spontaneous visits confirming exacerbation or missed AECOPD visit with medical record confirming AECOPD will be tabulated ([Figure 1](#), boxes 6 and 7).

CONFIDENTIAL

201112 (EPI-NTHI-001 BOD APA)
Statistical Analysis Plan Amendment 2 Final

Figure 1 Workflow of study assessment for AECOPD

CONFIDENTIAL

201112 (EPI-NTHI-001 BOD APA)
 Statistical Analysis Plan Amendment 2 Final

